Population	
Inclusion criteria for part 1 and 2:
 
 • Patients aged ≥ 18 years old • Patients with histologically/cytologically confirmed renal cell carcinoma (International Classification of Disease 10.revision (ICD)-10 C64) • Full medical information regarding all treatments before, during and after 1L should be available. 
Specific inclusion criteria only for Part 1:
 
 • Patients with locally advanced or metastatic disease and a start of any systemic 1L therapy against RCC between 01 January 2020 and 31 December 2021 
Specific inclusion criteria only for Part 2:
 
 • Patients with locally advanced or metastatic disease, who were treated with a combination of ICI + TKI or ICI + ICI as 1st line therapy against RCC and who had a completion of this therapy between 01 January 2020 - 31 December 2021 with a follow-up period of at least 3 months after completion of the 1L. 
Exclusion criteria for part 1 and 2:
 
 • Patients participating in an interventional clinical study within 30 days before start of 1L.
Outcomes	
The following clinical outcomes are of relevance in the study and should be answered regarding the research questions:
 
Primary Outcome
 
 ○ Progression-free survival in 1L in median and at defined timepoints after start 
Secondary outcomes

	
○ Overall survival rates from start of 1L therapy, expressed as median and at pre-defined timepoints○ Proportions of different therapy protocols used in 1L○ Best responses to 1L therapies○ Duration of response to 1L therapies○ Time-to-progression to 1L therapies○ Time-to-next-therapy to 1L therapies○ Frequency of modifications and discontinuations in 1L○ Reasons for modifications and discontinuations in 1L○ Treatment continuation after modifications and discontinuations in 1L (for all therapies and in relation to specific protocols like axitinib + avelumab or nivolumab + ipilimumab) 
Other Outcomes
 
○ Distribution of 1L therapy by age, gender and risk rating○ Distribution of 1L therapy and frequency of modifications/discontinuations by medical speciality and institution

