Study Size	Based on public data the population of patients with aRCC and an indication for a 1L therapy is around $n = 4.500 - 5.000$ patients per year (Robert Koch Institute 2020). In the period of 01 January 2020 – 31 December 2021, which is the main period of interest in the study for completing or starting 1L therapies, the total population of patients with aRCC would be around $n = 9.000 - 10.000$ patients. To estimate the needed number of patients in the study to reach adequate representation across Germany, the following common formula is used $n = \frac{z^2 \pi(1 - \pi)N}{z^2 \pi(1 - \pi) + E^2(N - 1)}$ 
N = population of patients with aRCC and indication for 1L = 10.000 patients in 24 months Π = 0,5 (consensus, if attribute is unknown before study) E = margin of error = 5% = 0,05 Z = 1,96 (for confidence interval of 95%)
 
Based on these assumptions (PFS of 1L therapies included in guidelines was 8.4 – 15.1 months in clinical studies) the number of patients needed for representative statement regarding the primary objective (= PFS rates at defined time points under real world conditions) is at least $n = 370$. With a buffer of around 10% the sample size in the study should be $n = 400$ patients with aRCC and 1L therapies in the period from 01 January 2020 – 31 December 2021. Based on published data for PFS it could be

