	
assumed for part 2, that also the number of patients with combination therapies in part 2 (n = 300) will grant a representative statement to all research questions. Based on information of urological and oncological experts as well as own data of the GermanOncology ^{*1} network (see below), the following assumptions could be set:
 
• Number of patients with new 1L in urological practices (per practice 1- 3 urologists) = 4 - 6 per year
○ Number of patients with new 1L in period of 24 months = 8 - 12• Number of patients with new 1L in oncological practices (per practice 2- 4 oncologists) = 4 - 6 per year
○ Number of patients with new 1L in period of 24 months = 8 - 12• Number of patients with new 1L in hospitals with urological focus = 8 - 12 per year
○ Number of patients with new 1L in period of 24 months = 16 - 24• Proportion of 1L therapies in urological and oncological practices: 50% : 50%• Proportion of patients treated with 1L in practices and hospitals (as most of therapies are oral therapies): 65% : 35% 
Based on the assumptions the needed number of sites are at least:
 
• Number of urological practices: 15• Number of oncological practices: 15• Number of hospitals with urological focus: 10• Total number of sites across Germany: 40 
<small>^{*1} GermanOncology operates a permanent network of 25 oncological practices across Germany, is collecting longitudinal RWE data about several tumor entities since 2012 and is able to analyze data from more than 25.000 patients with around 25 different tumor entities</small>

Data Analysis	
The following clinical outcomes will be measured:
 
Primary outcome:
 
○ PFS in 1L:
▪ described as median and rates of patients without disease progression or death for any cause at defined timepoints (6, 9, 12 and 18 months) after start of 1L therapy. 
Secondary outcomes:
 
○ OS in 1L

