	
 ▪ Defined as median and rates of patients alive at pre-defined timepoints (12 and 18 months) after start of 1L therapy. ○ Proportion of different drug regimen in 1L 
 ▪ Defined as percentages of therapy protocols used as 1L therapy. ○ Best response rate (RR) in 1L 
 ▪ Defined as best response (complete response (CR) / partial response (PR) / stable disease (SD) / progressive disease (PD) / not done (ND)) recorded from the start of the therapy until disease progression/recurrence based on investigator's assessment. A confirmation of response is not required. ○ Duration of Response (DoR) in 1L 
 ▪ Defined as time from documentation of first disease response to disease progression. ○ Time to progression (TTP) in 1L 
 ▪ Defined as time from start of therapy until objective disease progression without including deaths. ○ Time to next treatment (TTNT) in 1L 
 ▪ Defined as time from last drug administered to initiation of next therapy. ○ Dose modifications and discontinuations in 1L 
 ▪ Defined of number of patients with at least 1 dose modification (reduction of dose or cancelling of administration) or with an interim/permanent discontinuation of one or all drugs of a therapy. ○ Handling after dose modification or discontinuations in 1L 
 ▪ Defined as continuation of therapies after dose modifications or temporary/permanent discontinuation of single drugs. 
The clinical outcomes will be analyzed for the total group of all patients and for following subgroups:
 
 ○ Age: < 70 years vs. ≥70 years ○ Gender: male vs. female ○ Risk rating: favorable (low) vs. intermediate vs poor (high) risk ○ Medical disciplines: urology vs. medical oncology ○ Institutions: practices vs. hospitals
Milestones	
Planned milestones:
 
 ● Start of data collection: 1 October 2022 ● Interim analysis (expected): 31 October 2022 ● End of data collection: 30 January 2023 ● Final study report: 15 April 2023

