In the guideline of the German Cancer Society ([S3-Leitlinie Nierenkarzinom, AWMF, Nov 2021](#)) and of the German Society for Hematology and Oncology ([DGHO, May 2022](#)) for these patients combinations of pembrolizumab or avelumab with axitinib or pembrolizumab + lenvatinib or nivolumab + cabozantinib are recommended as the preferred first-line therapy for all risk groups (fig.2). As an alternative for patients with intermediate and high risk, the combination of nivolumab plus ipilimumab could be used. In patients ineligible for ICI and a low risk rating bevacizumab + INF, pazopanib, sunitinib or tivozanib, with an intermediate and poor risk rating cabozantinib and sunitinib are recommended.

Fig. 2: Guidelines for Treatment of Stage IV Renal Cell Carcinoma (DGHO May 2022 and German Cancer Society Nov 2021)

For subsequent therapies in case of progression, relapse, no response or intolerable toxicities the recommended first choices for 2L are nivolumab or cabozantinib or lenvatinib + everolimus. As alternatives or second choices, axitinib or sunitinib or everolimus or pazopanib or sorafenib are listed.

In the pivotal studies the effectiveness for the combinations of ICI + TKI wwa shown with PFS ranges of 15,1 – 23,9 months, with OS rates at 12 months of 89,9 – 91% and with objective response rate (ORR) ranges of 51,4 – 71% ([Bini TI et al, 2019](#); [Motzer R et al, 2019](#), [Motzer R et al, 2021](#)).

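### TTNT in 1L is counted from the last drug given, so it measures only the gap after 1L and has no time zero for Part 1 patients still on treatment

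*Combined protocol and SAP*

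**What the plan says.** In the abstract's outcome list TTNT appears by name only, as "Time-to-next-therapy to 1L therapies". The Data Analysis part of the abstract labels it as an outcome in 1L and defines it as "Defined as time from last drug administered to initiation of next therapy". Section 8.2 does not list it among the objectives, and section 9.6 adds no other definition.

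The neighbouring outcomes are anchored differently. PFS is given as a median and as rates of patients "without disease progression or death for any cause at defined timepoints", counted from the start of 1L. OS is counted from the same point. TTP is "Defined as time from start of therapy until objective disease progression without including deaths".

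On who is analysed, the Data Analysis part says "The clinical outcomes will be analyzed for the total group of all patients" and then lists subgroups. Section 9.1.1 admits a patient to Part 1 on having started any systemic 1L in 2020-2021. Part 2 requires a combination 1L completed in that period, with at least 3 months of follow-up afterwards. Section 9.6 defines evaluable patients by eligibility and at least one documented 1L application. Nothing limits TTNT to patients who have ended 1L, and no rule is given for death or for patients who receive no further therapy.

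**The concern.** An outcome presented as belonging to 1L, next to PFS and TTP, will be read as saying something about how long 1L served the patient. With the clock starting when 1L ends, it cannot do that. It is also hard to interpret in either direction: a short value may mean a prompt switch at progression, and a long one may mean a lasting response off treatment or a patient unfit for second line.

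The second problem is the risk set. A patient still receiving 1L has no last administration, so there is no date from which to count and the patient cannot enter even as a censored observation. In Part 1 the result would then rest on patients who had already stopped, in whom short courses of 1L are over-represented, without the plan saying so.

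**Working it through.** **The plan's own figure.** No figure is stated for TTNT. The sample size in section 9.4 reproduces: with z = 1.96, π = 0.5, E = 0.05 and N = 10,000, n = (3.8416 × 0.25 × 10,000) / (3.8416 × 0.25 + 0.0025 × 9,999) = 9,604 / 25.9579 = 369.98, i.e. 370. TTNT does not enter this calculation.

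**Time origins side by side** (section 4, Data Analysis).

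| Outcome | Clock starts | Clock stops |
|---|---|---|
| PFS | start of 1L | progression or death |
| OS | start of 1L | death |
| TTP | start of therapy | progression, deaths left out |
| TTNT | last drug given | start of next therapy |

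**What the definition measures.** Let D be the time from 1L start to the last 1L drug and G the time from that drug to the next therapy. TTNT as written equals G; counted from the start of 1L it would be D + G. For illustration:

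- Patient A: D = 20 months, G = 1 month. As written 1 month; from start 20 + 1 = 21 months.
- Patient B: D = 2 months, G = 1 month. As written 1 month; from start 2 + 1 = 3 months.

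**Who has a time zero.** Part 2 patients all do, because completion of 1L is an entry condition. Part 1 patients do only if they have stopped. The abstract's Variables part treats completion plus follow-up as a condition that a Part 1 patient may or may not meet, so the protocol itself allows for patients who have not completed 1L.

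**How many lack one.** This needs the distribution of time on 1L and the date to which patients are observed. The protocol gives neither firmly. As a sensitivity check, assume starts spread evenly between a and b months before the cut-off, and exponential time on 1L with median m. With λ = ln 2 / m, the share still on 1L is (exp(-λa) - exp(-λb)) / (λ(b - a)). PFS medians stand in for time on 1L: 8.4 and 15.1 months from the Study Size text ("PFS of 1L therapies included in guidelines was 8.4 – 15.1 months in clinical studies") and 23.9 months from section 8 ("PFS ranges of 15,1 – 23,9 months", for ICI + TKI).

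| Cut-off | a, b | m = 8.4 | m = 15.1 | m = 23.9 |
|---|---|---|---|---|
| 31 December 2021 | 0, 24 | 43.5% | 60.6% | 72.0% |
| 1 October 2022 | 9, 33 | 20.7% | 40.1% | 55.5% |
| 30 January 2023 | 13, 37 | 14.9% | 33.4% | 49.4% |

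The shares fall if patients stop before progression or if sites fill from the earliest starts, as section 9.1.2 asks. Section 9.4 implies 30 × 8-12 + 10 × 16-24 = 400-600 eligible patients. At 600, the 400 earliest starts cover 400/600 × 24 = 16 months. With that order, the last data-entry date (a = 21, b = 37) and a median time on 1L of half the 8.4-month figure (assumed), the share is 1.1%.

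These scenarios run from about 1% to 72%, too wide to serve as an estimate. The cut-off alone moves the result greatly, and the protocol is unclear on it. Section 9.5 describes documentation up to the present date, death or loss to follow-up, while the abstract's Study Design text limits capture to therapies running in 2020-2021.

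**The case against.** The strongest reply is that a gap between lines is a legitimate outcome, that its origin and event are stated explicitly, and that 1L duration, PFS and TTP are reported separately, so the 20- and 2-month patients would be told apart there. That is right as far as it goes. What it does not rescue is the label, which presents the gap as a 1L outcome, or the missing statement of who contributes.

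A reader might infer that "The clinical outcomes will be analyzed for the total group of all patients" flatly contradicts the TTNT definition. The documents do not support that reading. The sentence sets the whole sample against the subgroups, and it also covers outcomes that apply only to some patients, such as DoR ("Defined as time from documentation of first disease response to disease progression"), which needs a response, and handling after dose modification. Those outcomes name their condition, however; for TTNT the condition has to be worked out from the origin.

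A reader might also infer that a known and large share of Part 1 drops out. That is not supported either. The share depends on assumptions, and the requirement in section 9.1.1 for full treatment information before, during and after 1L could lower it further.

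Finally, section 9.6 leaves detailed methods to a SAP, which may modify the protocol's plans. Censoring rules could reasonably be settled there. But the time origin is not left open: the protocol states it, and an analyst who follows the protocol will use it.

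**Conclusion.** The point holds as a fault of definition. TTNT as written measures only the interval after 1L, and it has no time zero for Part 1 patients still on 1L, with no stated restriction to those who have ended treatment. This follows from the text alone and needs no distributional assumption. The number of Part 1 patients affected cannot be determined from the documents.

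The reach is limited to one secondary outcome that is not a listed objective. Part 2 patients do have an origin. The primary outcome and n = 370 stand. No data are lost, because Table 2 already captures 1L start and stop and the start of subsequent drug therapies. It is worth correcting before data collection, planned for 1 October 2022, but it does not threaten the study.

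**What to change.** Define TTNT as the time from start of 1L to start of the next therapy, and state:

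- whether the next therapy means systemic therapy only, which is what the subsequent-therapy row of Table 2 captures, or also surgery and radiotherapy, which section 8.2 counts among post-treatments. The wider meaning would need dates for those treatments after 1L, which Table 2 lists only as pre-treatments;
- how death before a next therapy is handled, for example as an event;
- that patients with neither event, including those still on 1L, are censored at last contact. Table 2 does not list a last-contact date, although section 9.5 suggests that the eCRF follows patients to that point, so this should be confirmed.

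If the present interval is wanted, report it separately as a treatment-free interval, only in patients who have ended all 1L drugs. Keep last administration as its origin, since section 9.7 treats end of therapy as a separate date. For combinations, state that this is the last dose of whichever 1L drug was stopped last.

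The cost is one reworded definition and one added descriptive line. With the systemic-only meaning, the dates of 1L start and next therapy are already planned.

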8.1. Primary Research Questions

Based on the above background, there are currently a number of unanswered questions for health services research:

- How is the effectiveness, defined as measurement of beneficial effects under “real world” clinical settings, (e.g. progression-free survival, overall survival and best response) of TKI and/or ICI as 1L in patients with aRCC?
- How are patients with aRCC treated in 1L under daily care conditions in Germany in general and in accordance to medical specialities (urology and medical oncology) and treatment settings (hospitals vs office-based practices)?
- Are all patients assigned to individual risk ratings under standard daily care conditions according to a scale developed by the IMDC before start of a 1L?
- How are patients treated in 1L in different risk rating groups and how is the adherence to national/international guidelines?
- What kind of previous and subsequent therapies are administered before and after 1L?
- How often are evaluations for PD-L1 expression performed before start of 1L and how many patients are positive (TPS $\geq 1\%$) or negative?

- How long are patients treated with TKI + ICI and ICI + ICI in 1L in general and in relation to specific therapies like avelumab + axitinib?
- How frequent are dose modifications and early discontinuations and what are the reasons?
- Are there differences in the handling of modifications among medical disciplines?

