8.2. Study Objectives

To answer these questions the following objectives are derived:

Primary Objective(s):

- Progression-free survival (PFS) for 1L therapies, expressed as median and as rates at timepoints of 6, 9, 12 and 18 months after start of 1L

Secondary Objectives:

- Overall survival (OS) of 1L therapies, expressed as median and rates at timepoints of 12 and 18 months after start of 1L therapy
- Best response in 1L overall and in dependence of administered drug regimen
- Progression-free survival of 1L therapies in dependence of specific drug regimen
- Pre- and post-treatments (i.e. surgery, radiotherapy, medicinal therapies) before/after TKI + ICI and ICI + ICI in 1L
- Duration of response (DoR) in 1L overall and in dependence of administered drug regimen (TKI + ICI or ICI + ICI)
- Frequency of dose modifications and temporary/permanent discontinuations of 1L therapies and their reasons
- Proportions of modifications by dose reduction compared to cancelling single applications
- Effectiveness (PFS, OS and best response) of administered 1L therapies under real world conditions by medical specialty (urology, medical oncology) and setting (practice, hospital)

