9.2. Variables

The following variables will be captured by a specific eCRF and are needed for the analysis of all outcomes and for answering all research questions.

Tab. 2: List of all variables, role, data source and operational definitions

Variable	Role	Data source(s)	Operational definition
Age and gender	baseline characteristic	Medical Chart	Years; male/female
Weight and body surface	baseline characteristic	Medical Chart	kg, m ²
Date of first diagnosis	baseline tumor characteristic	Medical Chart	dd/mm/yyyy
Stage and risk rating (IMDC) at first diagnosis and at start of 1L	baseline tumor characteristic	Medical Chart	Favorable risk / intermediate risk / poor risk
Assessments and results of PD-L1 expression as TPS	baseline tumor characteristic	Medical Chart	y/n; 0-100%
Non-medicinal pre-treatments (primary OP, cytoreductive nephrectomy radiotherapy)	baseline tumor characteristic	Medical Chart	y/n; dd/mm/yyyy of OP; mode of OP; intention of OP (curative/palliative); period and dose of radiotherapy
Medicinal pre-treatments (adjuvant, neoadjuvant)	baseline tumor characteristic	Medical Chart	y/n; start/stop and used therapy protocol
Location of administration and performing medical discipline	Relevant for outcomes	Medical Chart	Urological practice; hematological practice; hospital with urological department; hospital with oncological department
Administered drugs / protocols in 1L	Relevant for outcomes	Medical Chart	administered therapy protocol
If applicable: Reason for ineligibility of ICI	Relevant for outcomes	Medical Chart	Concomitant disease; patient's wish
Duration of 1L	Relevant for outcomes	Medical Chart	Start/stop of therapy or every cycle;

Dates of administrations for i.v. drugs in 1L	Relevant for outcomes	Medical Chart	Dates of every administration
Dosages per administration	Relevant for outcomes	Medical Chart	Dose of administered drugs per administration
Dose modifications or drug administration cancelling or interim/permanent discontinuations of single drugs / complete therapy in 1L	Relevant for outcomes	Medical Chart	Each for single/all drugs: Dose modification; cancelling single administration; temporare discontinuation; permanent discontinuation
Reasons for modifications, cancelling of single administrations and discontinuations in 1L	Relevant for outcomes	Medical Chart	Each for single/all drugs: intolerance; age; performance status; patient's decision; other

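### Dose modifications and discontinuations are pooled into one ever/never count with no exposure term, yet are to be reported by specialty and institution among patients with unequal time on treatment

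*Combined protocol and SAP*

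**What the plan says.** The Data Analysis row of section 4 defines the outcome as "Defined of number of patients with at least 1 dose modification (reduction of dose or cancelling of administration"), and continues "or with an interim/permanent discontinuation of one or all drugs of a therapy". It is therefore a single composite, scored once per patient, of modification and discontinuation. PFS and OS in the same row are tied to fixed months after start of 1L. This outcome has no time point, person-time denominator or censoring rule.

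The matching objective in section 8.2 is "Frequency of dose modifications and temporary/permanent discontinuations of 1L therapies and their reasons". Reporting by provider is explicit. The Outcomes row of section 4 lists "Distribution of 1L therapy and frequency of modifications/discontinuations by medical speciality and institution", and the subgroup list includes "Medical disciplines: urology vs. medical oncology" and practices versus hospitals.

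Part 1 takes any 1L started in 2020 or 2021. Part 2 takes ICI + TKI or ICI + ICI therapies completed in those two years (section 9.1.1). Table 2 in section 9.2 captures duration of 1L as "Start/stop of therapy or every cycle", dates of i.v. administrations, and four event types recorded for single or all drugs: dose modification, cancelled administration, temporary discontinuation and permanent discontinuation. Section 9.6 leaves detailed methods to a SAP that is not in the text available.

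**The concern.** A patient treated for longer has more opportunity to have a dose reduced or an administration cancelled. An ever/never proportion therefore combines how often modifications happen with how long patients were observed on treatment. If urologists and oncologists, or practices and hospitals, differ in regimen mix or time on 1L, their percentages can differ although their monthly rates are the same.

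Pooling adds a second difficulty. A permanent stop of all drugs counts as an event and also ends exposure, so the composite joins two components that relate to treatment duration in different ways. Section 7 puts particular emphasis on the handling of intolerabilities, so these percentages are likely to be among the study's most used results.

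**Working it through.** **The plan's own figure.** None is given for this outcome. The plan's one calculation, the sample size in section 9.4, reproduces: 0.9604 × 10,000 / (0.9604 + 0.0025 × 9,999) = 9,604 / 25.958 = 369.98, so 370. It does not bear on this point.

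**Is exposure unequal?** Part 1 starts span 24 months. With data collection from 1 October 2022 to 30 January 2023 (section 6), potential observation runs from about 9 months (start at the end of 2021) to about 37 months (start in January 2020). If the abstract's restriction to data from 2020 and 2021 is taken literally, it runs from almost nothing to 24 months. It is unequal on either reading.

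**Modification component: inputs**
- Median durations m of 8.4 and 15.1 months. This is the PFS range in the Study Size row of section 4, used as a proxy because the plan gives no treatment durations.
- 42% with at least one axitinib reduction on avelumab + axitinib (section 8), used for calibration.
- A monthly hazard of first modification λ, not in the documents, assumed constant and the same in both groups.

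**Formula.** With exponential treatment duration, μ = ln 2 / m and P(ever modified) = λ / (λ + μ). For m = 15.1, μ = 0.0459. Setting P = 0.42 gives λ = 0.42 × 0.0459 / 0.58 = 0.0332. For m = 8.4, μ = 0.0825, so P = 0.0332 / 0.1157 = 28.7%.

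| λ per month | m = 8.4 | m = 15.1 | gap (points) |
|---|---|---|---|
| 0.02 | 19.5% | 30.3% | 10.8 |
| 0.033 (calibrated) | 28.7% | 42.0% | 13.3 |
| 0.05 | 37.7% | 52.1% | 14.4 |
| 0.10 | 54.8% | 68.5% | 13.7 |

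If every patient is treated for exactly m months, P = 1 − exp(−λm). Calibration then gives λ = 0.0361 and proportions of 26% and 42%.

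**Early modifications.** If the hazard applies only in the first c months, P = λ/(λ+μ) × [1 − exp(−(λ+μ)c)]. For c = 3 or 6 and λ from 0.05 to 0.20, the pairs run from 12.4% versus 13.0% to 57.8% versus 62.7%. The gap is about 1 to 5 points, in the same direction.

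**Rate per patient-month.** In a simulation with λ = 0.05, first modifications divided by time at risk gave 0.050 per month in both groups, while the ever-modified proportions were 38% and 52%. Counting all modifications over all time on 1L behaves the same way under a constant rate: λT expected events over T months is λ.

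**Full composite.** A patient who stops early is an event. A patient treated for long and still on therapy without a modification is not. This can offset or reverse the pattern above, and the documents give nothing from which to compute the net effect. In Part 2 every patient has ended 1L. The definition does not exclude stops for progression or death, both of which Table 2 lists as reasons for end of 1L. If every end counts, the proportion approaches 100% in every subgroup and no longer discriminates.

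**The case against.** Much of the opposing case stands.

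- **Direction.** A reader might infer that groups with longer treatment look worse on the outcome as defined. That follows for modifications alone, not for the composite, because discontinuation is itself an event.
- **Regimen and Part 1 versus Part 2.** A reader might extend the point to these comparisons. Regimen is not in the subgroup list. The phrase "in relation to specific protocols like axitinib + avelumab or nivolumab + ipilimumab" belongs to continuation after a modification, a different outcome. Quotas by regimen in section 9.1.2 make such tables likely, but they are not listed for this outcome, and no comparison of the two parts is planned.
- **Handling.** The question "Are there differences in the handling of modifications among medical disciplines" in section 8.1 asks mainly what is done once a problem arises, which is not the ever/never frequency.
- **Size.** Fixed durations of 6, 12 and 18 months at 5% per month give 26%, 45% and 59% from 1 − exp(−0.05t). That spread comes from assumed durations and an assumed constant hazard. The documents' PFS range supports about 11 to 14 points, and far less if modifications come early.
- **Purpose.** Sections 4 and 8 quote the pivotal trials as ever/never percentages, so the crude count is needed for benchmarking. The study is descriptive and plans no test.
- **Deferral.** The separate SAP may add an exposure-adjusted measure. Table 2 also lists reasons for discontinuation apart from reasons for end of 1L, so the sponsor may intend to separate them. The definition does not say so.

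What remains is that the protocol plans a comparison by specialty and institution on a pooled count with no exposure term.

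**Conclusion.** The point holds as a worthwhile improvement to a secondary, descriptive outcome. For modifications alone, equal rates can appear as about 29% versus 42%. This assumes a constant, equal hazard, PFS as a proxy for duration, and specialties or institutions whose durations differ as widely as 8.4 and 15.1 months. The documents give no duration by specialty or institution, so bias in the planned comparison is possible rather than shown, and it shrinks to about 1 to 5 points if modifications are confined to the first 3 to 6 months. For the composite, neither direction nor size can be stated. Its possible approach to 100% in Part 2 depends on whether every end of therapy counts as a permanent discontinuation, which the text leaves open.

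**What to change.** - Keep the crude count for comparison with the pivotal trials.
- Report separately: (a) dose reduction or cancelled administration, (b) temporary discontinuation, (c) permanent discontinuation of one drug, and (d) permanent discontinuation of all drugs by reason, with stops for progression or death shown apart. Table 2 already captures these event types and the reasons for end of 1L.
- For the specialty and institution comparisons, add modification events per 100 patient-months on 1L from the start/stop dates. This needs no new field, provided the eCRF records each modification and not only yes/no.
- Show the rate beside the proportion, because the rate is neutral only if modifications occur at a steady pace. If every patient had exactly one early modification, fixed durations of 8.4 and 15.1 months would give 100/8.4 = 11.9 and 100/15.1 = 6.6 per 100 patient-months.
- Time to first modification, with ongoing therapy censored at last contact, is optional. Table 2 lists no modification date for oral drugs, so it would need one added field. Settle this before data entry, because section 9.3 rules out later queries.

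Cumulative incidence with end of 1L as a competing event should not replace the rate, since it still depends on duration. At 12 months with λ = 0.05, λ/(λ+μ) × [1 − exp(−12(λ+μ))] gives 30% versus 36% for medians of 8.4 and 15.1 months. End of 1L also cannot be a competing event when discontinuation of all drugs is the outcome.

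The cost is some extra analysis, and one date field only if time to first modification is wanted.
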